Autism spectrum disorder (ASD) is a neurodevelopmental disorder characterized by difficulties with socialization & reciprocal communication, along with restricted, repetitive behavior¹. An increasingly higher prevalence of ASD is documented in each successive epidemiological survey and is now estimated to affect more than 1% of youth². Social Deficits in Autism: Deficits in social interaction are the central feature of autism and often result in significant impairment in cognitively capable individuals with ASD. In light of the growing recognition of ASD in intellectually capable individuals of all ages, there is an acute need for effective treatment for social deficits. Although there are drugs proven to be effective in treating target symptoms of hyperactivity, irritability, & repetitive behaviors in ASD, to date, no medications have consistently been shown to reliably improve social impairments in ASD³⁻⁸. Earlier studies of fenfluramine, secretin, & naltrexone have largely been disappointing⁹⁻¹². Emerging evidence on the safety & efficacy of glutamatergic agents for the treatment of social deficits in ASD is encouraging. **Glutamatergic Dysregulation in Autism:** Glutamate (Glu) is the primary excitatory amino acid neurotransmitter in the brain. Glu, through its activity at N-methyl-D-aspartate (NMDA) receptors, is crucial for neurodevelopmental processes, including neuronal plasticity & higher cognitive functioning¹³. Over-activation of Glu is associated with excitotoxicity & apoptosis. Dysregulation in glutamatergic activity has been hypothesized to contribute to the pathophysiology of ASD¹⁴⁻¹⁵. Evidence for increased Glu activity in autism comes from serological, postmortem brain, and preliminary genetic studies¹⁶⁻²⁴. ¹HMRS in autism provides *in vivo* evidence of abnormal glutamatergic brain activity in autism by quantifying Glu levels in combination with glutamine (Gln) & gammaaminobutyric acid (GABA; Glu+Gln+GABA=Glx). Although no Glx abnormality was identified in the temporal lobes or anterior cingulate cortex (ACC) by 1.5 T ¹HMRS in preschool-age children with ASD lower levels of Glx were observed in grev matter by 3T ¹HMRS in older school-age children with ASD²⁵⁻²⁷. On the contrary, in adults with ASD, Glx levels are found to be higher in the amvadalo-hippocampal region (on 1.5 T ¹HMRS) and decreased in the right ACC (on 3T ¹HMRS)²⁸⁻²⁹. More recently, Harada & colleagues³⁰ specifically examined Glu metabolites at 3T ¹HMRS in children with ASD and noted no abnormality in Glu levels in the frontal lobe & lenticular nuclei. Taken together, previous ¹HMRS studies in autism suggest Glx dysregulation in various regions, including regions implicated in autism (i.e., medial temporal lobe [MTL] & ACC). Our ¹HMRS study in adolescent males with high-functioning ASD (HF-ASD) suggest significantly increased Glu in the ACC with no change in the bilateral MTL regions³¹. Role of Glutamate Modulators in the Treatment of Autism: Glutamatergic agents lamotrigine, amantadine, & D-cycloserine have been studied as potential treatments for symptoms of ASD. Lamotrigine attenuates Glu release by inhibiting voltage-sensitive sodium channels in the presynaptic neuronal membranes³². In a randomized-controlled trial (RCT) of lamotrigine in 28 children with ASD, although there was marked improvement in autism behaviors, an equally robust response to placebo (PBO) resulted in the lack of a statistically significant separation between the two groups³³. Amantadine, an antagonist at NMDA receptors, has also been studied in ASD. In a RCT of amantadine in 39 youth with ASD, amantadine was well tolerated and although

amantadine was not superior to PBO in treating hyperactivity & irritability per parent report, it was associated with significant improvement in inappropriate speech & illness severity on clinician-rated measures of response³⁴. D-cycloserine is a partial agonist at NMDA receptors³⁵. In a single-blind PBO lead-in trial D-cycloserine was well tolerated & was associated with significant improvement in social withdrawal³⁶. Thus, the empirical evidence for the efficacy of these glutamatergic agents for the treatment of social deficits in autism is modest at best. Memantine is a glutamatergic agent with a unique mechanism of action & the preliminary findings on safety & effectiveness are encouraging³⁷⁻³⁸.

Memantine: Memantine hydrochloride is a moderate-affinity, non-competitive, NMDA receptor antagonist. Memantine treatment in adults with Alzheimer's disease improves cognition, as well as functional & behavioral symptoms³⁹⁻⁴⁰. Available data from limited retrospective & prospective treatment studies of memantine in individuals with ASD report an acceptable tolerability profile with improvement in a range of behavioral impairments including attention, hyperactivity, language, eye contact, social interaction & withdrawal, & repetitive behaviors³⁷⁻³⁸.

Brain regions implicated in Autism: Several studies aiming to identify the etiology of autism have indicated involvement of limbic system structures including the amygdala, hippocampus, & the ACC⁴¹⁻⁴³. These limbic structures also show a high affinity for NMDA receptor binding. ACC: is functionally associated with information processing and response to emotional cues and is, therefore, a region of interest in autism. The ACC also has close anatomic connections to the amygdala & participates in emotional regulation. Lesions of ACC are known to cause blunted affect, disinhibition, disabling repetitive behaviors, & impaired social judgment including the inability to interpret social cues⁴⁴. Converging evidence from various investigative modalities suggests abnormalities in the ACC region in individuals with ASD including histopathological changes of increased cell packing density & decreased cell size, smaller in volume, decrease in regional cerebral blood flow, & metabolically less active^{34-35, 38, 39-40} with abnormal functional activity (theory of mind task related & resting state)⁴⁵⁻⁵². MTL: structures, the hippocampus & amvadala, play crucial roles in associative memory & social cognition, respectively, & lesions in the MTL are implicated in social impairments intrinsic to ASD⁵³⁻⁵⁵. Converging evidence of abnormalities in the MTL in ASD comes from various histopathological & imaging studies revealing decreased neuronal size and increased cell density and cytoarchitectural minicolumnar pathology, bilateral decreased volume & hypo-perfusion, and abnormal activation especially of amygdala on face recognition41,45-46,48, 55-65.

II. SPECIFIC AIMS

Primary Aims

Aim 1) To examine the clinical efficacy & tolerability of memantine for the treatment of social impairment in youth with ASD. We will study the short- & long-term clinical effects of memantine in 40 children and adolescents with ASD by conducting a 12-week randomized-controlled trial (RCT).

Aim 2) To examine the effect of memantine therapy on neural function in youth with ASD. We will assess neural response to memantine therapy by measuring spectroscopic

& resting state functional connectivity (RsFc) changes with memantine treatment. We will also assess association of neural & clinical response to memantine therapy.

Aim 3) To characterize neural functional deficits and/or abnormalities in youth with ASD by comparing ASD subjects to healthy control subjects undergoing the same spectroscopic & RsFc imaging with two scans 12 weeks apart.

III. LENGTH OF STUDY

This study may take up to 20 weeks from enrollment (allowing up to eight weeks to schedule and complete the initial screening process and baseline scan). Once subjects have completed the screening process and baseline characterization, subjects eligible for scanning will complete a baseline scan (for ASD subjects, this scan will be pre-treatment). ASD subjects will then begin the 12-week randomized-controlled trial. All subjects eligible for scanning, including healthy controls, will receive a follow-up scan approximately 12 weeks after the baseline scan. For ASD subjects, this scan will take place between the 10th and 12th week of treatment. All subjects will be taking the study medication at the time of the second brain scan. ASD subjects ineligible for scanning may participate in the 12-week randomized-control phase of the trial only.

IV. SUBJECT SELECTION CRITERIA

A. Inclusion Criteria (all participants)

1. Male & female subjects ages 8-18 years (inclusive).

Participants with ASD

- 3. DSM-5 ASD diagnostic criteria as established by clinical diagnostic interview
- 4. At least moderate severity of social impairment as measured by a total raw score of ≥85 on the parent/guardian-completed Social Responsiveness Scale-Second Edition (SRS-2)⁷¹ and a score of ≥4 on the clinician-administered Clinical Global Impression-Severity scale (CGI-S).

Healthy Control Participants

- 3. Age-, sex-, & IQ-matched with ASD participants.
- No Axis I diagnoses as established by the Kiddie Schedule for Affective Disorders and Schizophrenia—Epidemiological Version (K-SADS-E)⁷⁰ & confirmed by clinical diagnostic interview.
- 5. No significant traits of ASD as screened by SRS-2 (raw score <60).

Exclusion Criteria (all participants)

- 1. IQ ≤70 based on the Wechsler Abbreviated Scale of Intelligence-II (WASI-II) Vocabulary and Matrix Reasoning subtests
- 2. Impaired communicative speech
- 3. Subjects currently treated with the following medications (known to impact glutamate levels):
 - a. Lamotrigine
 - b. Amantadine

- c. N-acetylcysteine
- d. D-cycloserine
- 4. Subjects treated with a psychotropic medication not listed above on a dose that has not been stable for at least 4 weeks prior to study baseline.
- 5. Co-administration of drugs that compete with memantine for renal elimination using the same renal cationic system, including hydrochlorothiazide, triamterene, metformin, cimetidine, ranitidine, quinidine, and nicotine
- 6. Initiation of a new psychosocial intervention within 30 days prior to randomization.
- 7. Subjects who are pregnant and/or nursing.
- 8. Subjects with a history of non-febrile seizures without a clear and resolved etiology.
- 9. Subjects with a history of or a current liver or kidney disease.
- 10. Clinically unstable psychiatric conditions or judged to be at serious suicidal risk.
- 11. Subjects who meet on the K-SADS-E for alcohol or drug dependence or abuse. If the subject has a recent history of substance abuse, there will be a two-week washout period before initiating the trial as an added precaution. There are no known safety issues relating to memantine and recent history of substance abuse.
- 12. Serious, stable or unstable systemic illness including hepatic, renal, gastroenterological, respiratory, cardiovascular (including ischemic heart disease), endocrinologic, neurologic, immunologic, or hematologic disease.
- 13. Subjects with severe hepatic impairment (LFTs > 3 times ULN).
- 14. Subjects with genitourinary conditions that raise urine pH (e.g., renal tubular acidosis, severe infection of the urinary tract).
- 15. Known hypersensitivity to memantine.
- 16. Severe allergies or multiple adverse drug reactions.
- 17.A non-responder or history of intolerance to memantine, after treatment at adequate doses as determined by the clinician.
- 18. Investigator and his/her immediate family defined as the investigator's spouse, parent, child, grandparent, or grandchild.

Contraindications to MR scanning—braces, metal in the body, participant refusal to scan (e.g., due to severe anxiety or claustrophobia), etc.—are exclusionary for the scanning component of the trial. Subjects are allowed to have a security object (ei. ball or blanket) that is MR-safe and screened, in the scanner to help with possible anxiety they might experience due to the scanning. Healthy control subjects with contraindications to MR scanning will not be eligible to participate in the trial. However, in the event that an ASD subject with MR scanning contraindications otherwise meets all inclusionary criteria and does not meet any additional exclusionary criteria, that subject will be eligible to participate solely in the 12-week randomized-control phase of the study.

V. SOURCE OF SUBJECTS

We propose to enroll up to 60 subjects with ASD and 30 healthy controls for a total of 90 subjects. Up to 60 children and adolescents with ASD who exhibit marked social impairment will be enrolled in order to randomize 40 eligible subjects. In addition, up to

30 children and adolescents with no history of major psychiatric disorders, including ASD, will enroll in order for 20 eligible age-, sex-, & IQ-matched subjects to participate as neuroimaging healthy controls. Subjects will be recruited from the referral pool of existing and new patients at three different MGH sites – the Bressler Program for ASD, the Lurie Center for Autism, & the child psychiatry outpatient clinic – and from the general public by flyers and internet advertisements. Individuals who respond to local advertising will be screened for eligibility first by the study coordinator over the phone using an IRB-approved script prior to enrollment.

Subjects may also be recruited from our department's general pediatric screening research protocol, "A General Screening Protocol for Child and Adolescent Research Studies in the Pediatric Psychopharmacology Program" (2014-P-001103). After participating in the general screening protocol, subjects may be identified as potentially eligible for this study. In cases of potential eligibility, subjects and their parent/guardian will be informed of the study by their evaluating clinician. If they express interest in the study, the subject and their parent/guardian will be referred to this study's coordinator to schedule the first study visit, at which time a study clinician will review this study's informed consent and assent documents with the family. The screening protocol was designed so that some of its study procedures overlap with this study's screening procedures and that of other department studies. If a subject is referred from 2014-P-001103 and within the past 8 weeks, and there have been no changes in potential subject's medication or behavioral therapy, completed some of this study's required screening procedures under 2014-P-001103, we will use data previously collected so as to not burden the subject and/or their parent/guardian with redundant assessments.

In addition to the aforementioned sources, subjects for the healthy control arm of the study will be recruited from the pool of research subjects at the [name] Lab at MIT who have consented to being contacted for future research participation opportunities. Individuals will be phoned and screened for eligibility by the study coordinator using the IRB-approved script.

School representatives in the Boston and Belmont areas (e.g., principals or heads of the parent teacher organization/association) will also be approached via telephone or email and asked if study advertising materials can be brought to their school or placed in their school communications (e.g., newsletter). Only upon hearing back from the school representative will any recruitment materials be provided.

VI. SUBJECT ENROLLMENT

Informed consent/assent will be obtained prior to the performance of any protocol procedures and prior to administration of study drug for ASD subjects. The informed consent and assent documents will be used to explain, in simple terms, the risks and benefits of study participation to the subject and their parent/guardian. If a subject is of majority status, an investigator will obtain informed consent on the "Signature of Subject" signature line. The investigator will explain that "you and your child" and "your child" should be interpreted as applicable to the adult subject. Since this study involves

significant involvement of the parent, an investigator will also attain informed consent from a parent, who will sign the same consent form on the "Signature of Consent" signature line. The nature of the study will be fully explained to the subject and his/her parent/guardian by a board-certified physician who is either the principal investigator or a co-investigator. The subject and his/her parent/guardian will be encouraged to ask questions pertaining to their participation in the study and the subject and his/her parent/guardian may take as much time as they feel necessary to consider their participation in the study, as well as to consult with family members or their physician. Participation in this study is voluntary and the subject and/or his/her caretaker may withdraw the subject from the study at any time. The IRB-approved informed consent/assent documents will be signed and dated by the subject's parent/guardian, the subject, and the physician obtaining consent.

VII. STUDY PROCEDURES

This study includes two components: a 12-week randomized-controlled trial of memantine for the treatment of Autism Spectrum Disorder, and two ¹HMRS scanning sessions pre- and post-treatment.

After providing written informed consent and assent, all subjects will complete a clinical diagnostic interview with a study clinician to assess eligibility. All subjects will be administered a detailed assessment battery including a brief demographic interview, a pre-MR checklist to rule out contraindications to scanning, an indirect structured diagnostic interview (K-SADS-E), the SRS-2, and the following assessments to assess cognitive capabilities: WASI-II, the Wechsler Intelligence Scale for Children (WISC-IV; 8-16 year olds) and the Wechsler Adult Intelligence Scale (WAIS-IV; 17 and 18 year olds only) to assess cognitive capabilities.

If both parents of the subject are available, we will ask each parent to independently complete an SRS-2 form. Both forms will be scored, and the form with the higher score will be used to determine subject eligibility in order to reduce the possibility of under-recognition of ASD symptoms.

All participants will be required to give a urine sample to test for certain types of drugs. This includes prescription drugs, illegal drugs (street drugs), and controlled substances (substances that may be habit forming) that may affect behavior and that may be regulated by law. Results of the drug screen will be conveyed to the participant by the study clinician and if the results are positive for drug(s) there will be further discussion with the participant to determine if they are appropriate to participate in the trial.

In addition, female ASD and control subjects of childbearing potential will have a urine pregnancy test. If a participant has a positive urine pregnancy test, she will not be able to take part in the study. The study doctor will inform the participant of any positive test results. The decision whether to inform the subject's parent/guardian of these results will be made by the study doctor based on the participant's age and maturity level.

ASD subjects will also be assessed the Autism Diagnostic Observation Schedule (ADOS)⁶⁸. This assessment is recommended, but due to limited ADOS rater availability, it will only be performed if time and schedule of participant and ADOS rater permit. If

determined clinically necessary by study physician, the Clinical Evaluation of Language Fundamentals-Fourth Edition (CELF-4). ASD subjects will complete physical assessment measures (complete physical examination, tanner staging, vitals, height, ECG, and blood screening tests). If a subject refuses a blood draw during the screening visit due to extreme fear and anxiety, they will not be asked to provide a blood sample at the completion visit. For a complete schedule of assessments, refer to the Table I (page 18). The screening process may take place over multiple days, as necessary.

We anticipate that subjects may enter this study following completion of/withdrawal from other ASD protocols in our office, and that there may be procedural overlap. So as to not burden subjects/parents/guardians with redundant time commitments, we will use the following diagnostic data previously collected. If a subject has completed an evaluation with one of the study clinicians and/or the structured diagnostic assessment in the three years prior to entrance into this study, he/she will not be asked to repeat any overlapping diagnostic procedures. We will use the study diagnostic data that had been previously collected so as to not burden the subject with redundant time commitments. However, the study clinician will review the interval time period to assess for clinically significant medical or psychiatric history, to ensure that the subject meets appropriate study entrance criteria.

If a subject has been assessed with the WASI-II or WISC-IV/WAIS-IV in the 12 months preceding their entrance into this study, subjects will not be asked to repeat these procedures. We will use the data previously collected so as not to burden the subject with redundant time commitments.

All data will be collected and entered into StudyTRAX, an electronic data capture system that streamlines data collection and ensures data integrity. StudyTRAX software allows researchers to design and implement study surveys electronically for collecting, storing, retrieving, and manipulating data.

Parents/guardians and/or research staff will enter survey responses into electronic assessment forms using computers at the research site. The responses will then be transmitted securely via an encrypted connection and stored in a secured database. Electronic data capture eliminates the need for subsequent data entry by staff, thus minimizing human error. However, in the event that StudyTRAX is unavailable or malfunctioning, study staff will print all study instruments and study data will be collected in paper form.

12-Week RCT (ASD Subjects only):

Participating children and adolescents with ASD who meet the eligibility criteria will be randomly assigned to either memantine or placebo for the course of the 12-week RCT. Subjects will be assessed weekly during the titration phase (Weeks 1-4) & during the maintenance phase at midpoint (Week 6), Week 9, & at completion (Week 12/early termination). The same caretaker (a parent/guardian most familiar with the subject's day-to-day behavior) will participate in the assessment of behavioral symptoms at all visits of the treatment phases.

Randomization: The MGH Clinical Trials Pharmacy will prepare the blinded

memantine and placebo capsules for the study. ASD subjects will be randomized to either active memantine or placebo in a 1:1 ratio after they have been determined to meet all eligibility criteria. Randomization lists stratified by gender and racial/ethnic minority status (minority vs. Caucasian) will be generated by the statistician & passed to the investigational pharmacy for assignment.

Washout Period: ASD subjects who are currently being treated with prohibited psychotropic medications as listed in the exclusion criteria must discontinue the use of their medication to be eligible for participation in this study. Medication washout is recommended by our clinicians to participants, their parent/guardian, and current providers – this is done based on a case-by-case assessment, considering the duration on drug, the dose, and the adverse effects associated with the treatment and effects of stopping that medication/treatment. Our office does not take over care for the patient, but remains available during this time period. The washout schedule –which will span two weeks or more -- will be discussed with the participant, their parent/guardian, and current providers. Individuals taking a medication that is effectively and safely treating their symptoms will not be taken off of such medication for the purpose of enrolling in this study.

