We also predict normalization of brain activity measures with memantine treatment. "Normalization" will be defined as having achieved a resting state functional connectivity level that is no more extreme than the 95th percentile of the control distribution. Normalization ratings between the memantine and PBO groups will be compared using a logistic RMs. A significant effect would mean an increased likelihood of normalization in memantine-treated subjects.

To test our hypothesis of a significant association between neural and clinical response and between glutamate and functional connectivity response, we will use endpoint clinical efficacy scores as the dependent variable and change in brain activity measures from baseline to endpoint as the independent variables. For our exploratory hypothesis examining neural biomarkers of response to memantine therapy, we will use a GLM with endpoint clinical efficacy scores as the dependent variable, baseline brain activity measures as the independent variables, and baseline clinical scores as a covariate.

Resting state data will be analyzed using a seed driven approach with custom software (Conn)⁸⁸. Data will be slice time corrected, realigned, coregistered, normalized, and spatially smoothed as necessary. Physiological & other spurious sources of noise

will be estimated using the CompCor method, and removed together with movementrelated covariates. The residual BOLD time-series will be band-pass filtered over a lowfrequency window of interest (0.009Hz<f<0.08Hz). Correlation maps will be produced by extracting the residual BOLD time course from bilateral anatomically defined amygdala (WFU_Pickatlas) seed regions, and computing Pearson's correlation coefficients between that time course and the time course of all other voxels. Correlation coefficients will be converted to normally distributed scores using Fisher's transform to allow for second-level General Linear Model analyses. Between group differences will be calculated for each ROI.

Power Considerations

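### Aim 3 compares ASD subjects who may be on stable psychotropics with controls who are very probably unmedicated, and no planned analysis separates medication from diagnosis

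*Combined protocol and SAP*

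**What the plan says.** Aim 3 is listed among the primary aims (II. Specific Aims). It characterizes functional abnormalities in ASD by "comparing ASD subjects to healthy control subjects undergoing the same spectroscopic & RsFc imaging", with two scans 12 weeks apart.

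The medication rules are in IV. Subject Selection Criteria, in the exclusion list for all participants:
- Exclusion 3 removes "Subjects currently treated with the following medications (known to impact glutamate levels" and names lamotrigine, amantadine, N-acetylcysteine and D-cycloserine.
- Exclusion 4 removes subjects on a "psychotropic medication not listed above on a dose that has not been stable for at least 4 weeks prior to study baseline". A psychotropic outside the four, at a stable dose, is therefore allowed.
- The washout paragraph in VII. Study Procedures adds: "Individuals taking a medication that is effectively and safely treating their symptoms will not be taken off of such medication" in order to enrol.

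For controls the psychiatric criterion is "No Axis I diagnoses as established by the Kiddie Schedule for Affective Disorders and Schizophrenia" (Epidemiological Version), confirmed by clinical interview. V. Source of Subjects adds that they have no history of major psychiatric disorder. They are matched to ASD participants on age, sex and IQ.

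In VI. Biostatistical Analysis (Neuroimaging Data Analysis), the covariates named are the pretest brain measure and, in one exploratory biomarker model, baseline clinical scores. For connectivity the text says "Between group differences will be calculated for each ROI", with no covariate. Table I shows concomitant medications collected in both ASD and control subjects.

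**The concern.** Aim 3 is an observational contrast inside a randomised trial, so randomisation gives it no protection. If psychotropic use is common in the ASD group and close to absent in controls, the raw difference mixes the effect of having ASD with the average effect of the drugs that ASD subjects take. A positive finding could be medicated versus unmedicated rather than ASD versus healthy. A drug effect in the opposite direction could hide a real ASD difference.

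Medicated ASD subjects are foreseeable. Recruitment includes a child psychiatry outpatient clinic, and the section on secondary outcomes notes that ADHD, anxiety and depression features often accompany ASD. Exclusion 3 shows that the sponsor already accepts that background drugs can disturb a brain measure.

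**Working it through.** **The plan's own figures.** Power Considerations gives power of 0.55, 0.43 and 0.51 for d = 1.20, 1.03 and 1.15 with 7 ASD and 7 control subjects. A two-sample noncentral-t calculation at two-sided 5% (the plan states no alpha) gives 0.541, 0.426 and 0.507, so these reproduce within rounding. The 95% connectivity power for 40 v 20 comes with no effect size and cannot be checked directly. Solved backwards at two-sided 5%, it needs d of about 1.00.

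**Inputs for the check.**
- From the plan: 40 ASD subjects and 20 controls.
- Assumed, because the documents give neither: p, the share of ASD subjects on a psychotropic, and s, the drug effect on a brain measure in SD units.
- Also assumed: no true ASD effect, all controls unmedicated, two-sided 5%.

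**Formulas.** Expected spurious difference = p × s. Standard error of a standardised difference = sqrt(1/40 + 1/20) = 0.274. Noncentrality = p × s / 0.274, on 58 df. The last column is a simulation that also includes the extra variance from mixing medicated and unmedicated subjects.

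| p | s | p × s | noncentrality | false positives, formula | false positives, simulated |
|---|---|---|---|---|---|
| 0.25 | 0.3 | 0.075 | 0.27 | 5.8% | 5.8% |
| 0.25 | 0.5 | 0.125 | 0.46 | 7.3% | 7.1% |
| 0.50 | 0.5 | 0.250 | 0.91 | 14.6% | 13.9% |
| 0.50 | 0.8 | 0.400 | 1.46 | 30.1% | 27.4% |

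N = 40 is an upper bound, since ASD subjects with MR contraindications may join the drug trial only. If 30 were scanned, the standard error would be sqrt(1/30 + 1/20) = 0.289, and the last two rows by formula would become 13.6% and 27.4%.

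**Effect of adjustment.** Fit diagnosis plus an any-psychotropic indicator. With no medicated controls there are three cells (controls, unmedicated ASD, medicated ASD) and three parameters. The diagnosis coefficient is then exactly mean(unmedicated ASD) minus mean(controls). In simulation with s = 0.8, its false-positive rate is 4.8% to 5.0% at 25%, 50% and 75% medicated.

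**Cost in precision.** With n unmedicated ASD subjects the standard error is sqrt(1/n + 1/20). Power below is for a plain two-sample test of unmedicated ASD v 20 controls at d = 1.0:

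| n | standard error | power |
|---|---|---|
| 40 (all ASD, unadjusted) | 0.274 | 95% |
| 30 | 0.289 | 92% |
| 20 | 0.316 | 87% |
| 10 | 0.387 | 70% |

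The covariate model pools residual variance over all 60 subjects (57 df) and gives slightly more at n = 10: 72%.

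**The case against.** The strongest defence is that the protocol already protects the spectroscopy: it bars four drugs precisely because they affect glutamate. That stands in part for Glu. The list covers only those four agents, and its stated reason is glutamate, so it was not designed to protect connectivity, the other half of Aim 3.

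Second, unmedicated controls are not a stated fact. Exclusion 4 applies to all participants, and no criterion bars a control from a stable psychotropic. That is correct; it is a strong inference from the no-Axis-I rule.

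Third, nothing in the documents says that other psychotropics change Glu or these connectivity measures, and at the low end of the range the error rate is close to nominal. Both points are fair. They make this a possible bias of unknown size, not a demonstrated one.

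Fourth, medication may follow severity or comorbidity, so unmedicated ASD subjects may not represent ASD in general. This stands and limits what adjustment can achieve.

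Two stronger readings are tempting, and neither is supported:
- A reader might infer that a medication covariate cannot help because almost no control is medicated. The three-cell argument shows the opposite: the adjusted diagnosis effect is the unmedicated-ASD comparison itself.
- A reader might infer that the memantine normalization result is biased too, because it is judged as "no more extreme than the 95th percentile of the control distribution". That test compares randomised arms against one common cutoff, and background medication is balanced between them in expectation. It adds noise or chance imbalance there, not systematic bias.

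**Conclusion.** The concern holds for the Aim 3 ASD-control contrast. As written, the plan lets a background drug effect be reported as an ASD abnormality, or mask one, and it leaves unused the medication data that could show which. The false-positive rate runs from about 6-7% (25% medicated, 0.3-0.5 SD) through about 15% (50%, 0.5 SD) to about 30% (50%, 0.8 SD). These figures rest on an assumed share medicated, an assumed drug effect, unmedicated controls, and all 40 ASD subjects being scanned. Exposure is probably smaller for Glu than for connectivity because of exclusion 3.

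The plan also does not say which scan supplies the cross-sectional contrast. At the second scan the ASD subjects are on memantine or placebo, which adds a further drug difference from controls. The efficacy analysis and the randomised imaging comparisons are unaffected. The change is worth making because it is cheap and alters what a primary aim can conclude.

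**What to change.** In the Neuroimaging Data Analysis section:
1. Define the baseline (pre-treatment) scan as the data for the Aim 3 cross-sectional contrast.
2. For each Aim 3 measure, report beside the all-ASD comparison the diagnosis effect from a model with diagnosis and any-psychotropic use at the baseline scan, with its confidence interval. With unmedicated controls this equals unmedicated ASD v controls. Also report medicated v unmedicated within ASD.
3. Tie the wording to the result. Call a difference an ASD abnormality only with the adjusted estimate and interval beside it. If that estimate is near zero or reversed, describe a difference in a partly medicated ASD sample.
4. State that medication may track severity or comorbidity, so adjustment does not remove all confounding.

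The cost is a few lines of analysis plan and two extra analyses on data that Table I already collects; no eligibility or treatment rule changes. The adjusted estimate is less precise: at d = 1.0, power is about 92%, 87% and 70% with 30, 20 and 10 unmedicated ASD subjects.
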